2. BACKGROUND AND RATIONALE

2.1 Background on Condition, Disease, or Other Primary Study Focus

Tobacco use continues to be a leading preventable cause of death in the United States accounting for about 480,000 deaths each year (USDHHS, 2014). For every death related to smoking-related diseases there are 30 people who suffer from serious illnesses directly related to smoking that include stroke, chronic obstructive pulmonary disease, heart disease, and lung cancer. According to a recent report by the Surgeon General, the total economic cost of tobacco use in the United States was \$289 to \$332 billion from 2009-2014.

2.2 Study Rationale

Several meta-analytic reviews have shown that proactive telephone-based tobacco cessation services are an effective way to reduce cravings for and use of tobacco (Fiore et al., 2008; Hopkins et al., 2001; Lichtenstein et al., 2010). Telephone Quitlines (QLs) are an efficient, centralized, and highly scalable way to help individuals quit their use of tobacco that are available in all fifty states plus the District of Columbia. The North

American Quitline Consortium reported that 515,000 users, or 1.2% of all smokers, contacted QLs in 2009: this represents an increase of 129.7% since 2005. In Arizona, the Arizona Smokers' Help Line (ASHLine) is run through the University of Arizona, Mel and Enid Zuckerman College of Public Health, and is funded by the State of Arizona, Department of Health. The ASHLine, where the proposed study will be implemented, enrolled 10,824 individuals from July 2013 to June 2014, which represented a 7% increase from the previous year. Of these, about 73% were Caucasian, 57% were female, 17% were Hispanic, 8% were African American, and 2% were American Indian. The ASHLine uses a "Coaching Model," and reported an average of 3.9 calls per enrollees--two calls for medication only enrollees, and nine calls per coaching enrollees.

Researchers have also demonstrated the cost-effectiveness of telephone QLs in the United States and Europe over the past 25 years (Cromwell, Bartosch, Fiore, Hasselblad, & Baker, 1997; Fiore et al., 2008; Kahende, Loomis, Adhikari, & Marshall, 2009; Lichtenstein et al., 2010). Despite these findings, many state agencies that oversee the implementation of QLs are cutting funds at a time when there is record utilization of services (NAQC, 2010). This situation has prompted many state sponsors to try to improve their effectiveness by focusing recruitment on under-represented groups and reducing human capital with increased web-based services: approximately 1/3 of US QLs include some type of internet service to supplement counseling. Theoretically-based website services and alternative intervention approaches that are more appealing to diverse groups may increase the reach, engagement, and effectiveness of QLs.

Guided imagery is a mind-body technique that involves the visualization of mental images and is similar to mindfulness meditation (MM). Both mindfulness meditation and mental imagery can create awareness and direct attention to one's thoughts, feelings, and health behaviors. Guided imagery and other mindfulness interventions can effectively assist tobacco users to quit (Brewer et al., 2011; Wynd, 2005; Zernig et al., 2008). One randomized controlled trial with 779 adult smokers compared the use of bupropion with brief psychotherapy that was taught to participants over 2 days lasting 8 hours (Zernig et al., 2008). The latter condition consisted of exposure to guided imagery intended to enhance self-management, decidedness, assertiveness, selfdetermination, and self-assurance. Intent-to-treat analysis showed 12-month abstinence rates of 39.1% and 12.3% for the psychotherapy and bupropion groups, respectively. These rates were 39.9% (psychotherapy) and 22.5% (bupropion) for those who completed the study. In another four week randomized controlled trial, 33 adults were taught mindfulness and encouraged to practice at home (Elwafi et al., 2013). Results showed that home practice predicted reduced cigarette use, and informal mindfulness practice moderated the relationship between craving and cigarette use (Elwafi et al., 2013). Another smaller trial compared those receiving education and counseling with education/counseling plus imagery training (Wynd, 2005). Results of that study indicated abstinence rates of 12% and 26%, respectively (Wynd, 2005). These studies support the efficacy of guided mental imagery for smoking cessation.

However, these studies employed in-person interventions that are prohibitively expensive and limit larger scale implementation and overall reach. Combining the use of guided imagery with tobacco QL services offer a highly scalable, innovative, and a cost-effective strategy for delivering a guided imagery intervention. We will develop, using input from expert consultants, a community advisory board, and our target population, a guided imagery intervention, attention-control condition, and recruitment strategies. The intervention has little potential risk and may increase the use of telephone-based tobacco cessation counseling by male and racially-/ethnically-diverse smokers.

3. STUDY DESIGN

As shown in Figure 1, we will use a two-group randomized control design. Participants will be recruited through IRB-approved flyers and advertising, and the ASHLine, screened for eligibility by ASHLine or study staff, consented by ASHLine or study staff, administered the baseline survey by ASHLine or study staff, and automatically randomized by the REDCap system (using a randomization algorithm) to either the Imagery Intervention (IIC) or Control (CC) Condition. We will enroll and randomize up to 120 feasibility trial participants (approximately equal numbers per condition).

Participants in both conditions will receive a screening call and 6 telephone coaching sessions delivered over 6 weeks by trained ASHLine or project staff. The screening call will be conducted by ASHLine or study staff to assess study eligibility, collect consent for study participation, and collect baseline survey items. The coaching sessions will be approximately 20-50 minutes long. We will develop baseline survey items to be administered to participants during the screening call. We will develop content for each coaching call for each study condition, including instructions for using the study website. The IIC sessions 1-4 will include an introduction to guided imagery, setting a quit date, setting a guided imagery schedule, and helping the participant develop a guided imagery script which the coach will record as an audio file and send to the participant to listen to. Sessions 5-6 will focus on quitting issues and relapse prevention. The CC sessions 1-4 will include an introduction to cognitive behavioral telephone coaching, setting a quit date, an introduction to the quitting booklet [in development], and setting a schedule for using the booklet, and assistance in developing the first part of the quit plan. Sessions 5-6 will focus on quitting issues and relapse prevention strategies. Sessions 2 – 4 will review progress and build skills according to study condition, culminating in a quit day at approximately 4 weeks post-enrollment. Sessions 5-6 will reinforce quitting smoking or help participant recommit to quit. Between sessions, participants in both conditions will receive occasional text messages (e.g. motivational messages, call reminders). During the enrollment process participants are asked for a phone number at which they can receive texts. By providing the number they are agreeing to receive occasional texts. During the coaching sessions, the coach asks the participant if they wish to receive more messages (e.g., motivational messages, tips for quitting, etc.).

Participants in both conditions who request it will receive up to 4 weeks of Nicotine Replacement Therapy (NRT), either nicotine patches or lozenges based on level of nicotine

dependence. All participants requesting NRT will be screened by trained project staff for contraindications for use, assessed for level of dependence, and informed of potential side effects (AEs and SAEs) of using NRT. The screening, assessment, and informational scripts are under development and will be submitted to the IRB for approval prior to these activities occurring with participants.

Participants will be assessed by project staff at 8-weeks and 6-months post-enrollment. Self-report surveys will be administered online or by phone. All participants who report abstinence at the 6-month assessment will be asked to perform a biochemical validation. Biochemical validation will be performed via saliva test kit sent to the participant's home and a video chat with University of Arizona project staff.

The primary outcome will be self-reported tobacco abstinence. We will measure 7-day point prevalence, 30-day point prevalence and prolonged abstinence at each follow-up assessment. We hypothesize that participants in the Imagery Intervention Condition will report equal or higher rates of cessation than those in the Control Condition.

Our feasibility outcomes include: at least 50% of participants will complete the 6-session intervention program; 50% will report listening to the guided imagery audio files at least 5 times per week; and 50% will use the website at least one time; and 75% of participants will complete both follow-up assessments.

Secondary outcomes will include increased number of quit attempts, reduced tobacco use (for non-quitters) and increased self-efficacy for quitting. We hypothesize that participants in the Imagery Intervention Condition will report equal or lower levels of tobacco use, and equal or higher levels of quit attempts and self-efficacy for quitting.

In addition, we will explore the demographics of study participants to assess how they may differ from the general population of ASHLine callers. Our goal is to increase the diversity of ASHLine callers.

[figure not shown]

Figure 1. Study Flow Diagram - Minimum Number of Participants Noted, Up to 120 (60 Per Condition) Will be Randomized

4. SELECTION AND ENROLLMENT OF PARTICIPANTS

Participants will be male and female smokers over the age of 18 who are interested in quitting and call the ASHLine or respond to flyers or advertising. During the study period, we will actively recruit underrepresented smokers to call the ASHLine. The ASHLine has agreed to display tailored recruitment information on their website (as developed by our consultants and community advisory board [CAB]), and we will employ additional recruitment strategies (e.g., swap meets, churches, medical providers, identified by the CAB and consultants) to attract diverse potential participants. Additional participant recruitment may occur through the Arizona ASHLine using special features on their study website (see Figure 2). ASHLine staff may embed a link about the research study that will be tailored for racially- and ethnically-diverse audiences and feature content about the use of guided imagery.

4.1 Inclusion Criteria

Participants must meet all of the inclusion criteria to participate in this study.

Inclusion Criteria:

- Current smokers or those whose primary tobacco product is cigarettes (e.g., dual cigarette and smokeless tobacco users).
- Current callers and former callers who have not enrolled in the ASHLine for the previous 12 months
- At least 18 years of age
- Have email access
- Speak English
- Ability to understand study procedures and to comply with them for the entire length of the study.
- Contraception is not necessary or required.

4.2 Exclusion Criteria

All candidates meeting any of the exclusion criteria at baseline will be excluded from study participation.

Exclusion Criteria:

- Individuals with serious mental illness
- Tobacco users who have used the ASHLine in the past 12 months
- Tobacco users who are currently receiving any form of tobacco cessation treatment
- Refusal to be randomized to one of the study conditions.

4.3 Study Enrollment Procedures

The REDCap system will be used to document information during all phases of the study. The REDCap system will track the name and contact information of the participants, date of contact with ASHLine or study staff, the staff person who took their telephone call, eligibility/screening information, consent, baseline survey, and randomization information. Informed consent will occur over the telephone with ASHLine or study staff reading an IRB-approved abbreviated version of the consent document to participants. Participants will provide verbal consent and be emailed a copy of the full-length consent form for their records. Upon completion of informed consent, ASHLine or study staff will administer the baseline survey via the phone. Upon completion of the baseline survey, the data from ASHLine 2.0 will be transferred to the REDCap system. Study staff will then call the participant and confirm consent. The REDCap system will be used to randomize the participant to either the IIC or CC. The REDCap system will automatically assign the participant to condition using a randomization algorithm. Following randomization, study staff will assign the participant to an appropriate study coach. The coach will then schedule the first session with the participant.

5. STUDY INTERVENTIONS

5.1 Interventions, Administration, and Duration

The Imagery Intervention will consist of 6 weekly telephone coaching sessions delivered by trained project staff plus a companion website containing study materials. As shown in Table 2, the first session will include an overview of guided imagery, setting a quit date, setting a guided imagery schedule, description of the Intervention website and instructions for using the website. Sessions 2-4 will include follow-up and review of progress and use of the imagery files. Session 5 will include instructions using / modifying the guided imagery script. Session 6 will review progress and creating a plan for continued use of guided imagery for relapse prevention and/or cessation.

Week 1-Imagery Intervention Condition	Week 1-Control
Table 2. Activities in the Intervention and Control Cond	itions by Week

Week 1-Imagery Intervention Condition	Week 1-Control Condition
Theme: Intro and planning	Theme: Intro and planning
Goal: Set quit date, define GI, determine	Goal: Set quit date, determine reasons/benefits of
reasons/benefits of quitting, create script and set times	quitting and set time to do portion of booklet.
to practice script.	Content: Define and discuss behavioral treatment.
Content : Basic definition of GI, intro to breathing,	Discuss previous quit attempts.
relaxation. Draft one GI sentence for each	
reason/benefit.	
Week 2-IIC	Week 2-CC
Theme: Triggers	Theme: Triggers
Goal: Develop GI strategies to address triggers.	Goal: Develop behavioral strategies to address
	triggers.

Content: Identify participant's primary trigger and	Content: Review triggers and coping strategies
coping strategy; develop script. Practice previous	participant identified in booklet. Recommend
script and this one together.	practicing new coping strategy in the trigger setting
	each day.
Week 3-IIC	Week 3-CC
Theme: Cravings and Withdrawal	Theme: Cravings and Withdrawal
Goal: Have client understand 2 types of urges	Goal: Have client understand 2 types of urges
(habitual and physiological reaction). Develop	(habitual and physiological reaction). Develop
strategies to address cravings and withdrawal. Discuss	strategies to address cravings and withdrawal. Discuss
NRT.	NRT.
Content: Create script to manage cravings and	Content: Identify replacement behaviors for cravings
withdrawal. Make listening to GI a new habit.	and withdrawal issues.
Week 4-IIC (On or slightly before quit date)	Week 4-CC (On or slightly before quit date)
Theme: Handling withdrawal and preparing to quit	Theme: Handling withdrawal and preparing to quit
Goal: Determine strategies to handle withdrawals,	Goal: Determine strategies to handle withdrawals,
discuss use of NRT and quit preparation.	discuss use of NRT and quit preparation.
Content: Make edits or additions to script if	Content: Review strategies previously identified and
necessary. Practice entire script throughout week, or	any new ones, as needed.
just a portion if too long.	
Week 5-IIC	Week 5-CC
Theme: Relapse prevention/recommit to quit	Theme: Relapse prevention/recommit to quit
Goal: Support quitting among those who quit and	Goal: Support quitting among those who quit and
encourage quitting among those who didn't or who	encourage quitting among those who didn't or who
relapsed.	relapsed.
Content: Check whether participant wants any	Content: Revise behavioral strategies as needed to
changes to the script. If so, identify changes and re-	cope with anything that came up during the week.
record.	
Week 6-IIC	Week 6-CC
Theme: Relapse prevention/recommit to quit	Theme: Relapse prevention/recommit to quit
Goal: Prepare participants to be successful on their	Goal: Prepare participants to be successful on their
own. Give post-quit resources.	own. Give post-quit resources.
Content: Revise script if necessary. Provide GI and	Content: Revise behavioral strategies if needed.
relaxation resources.	
8 Week Follow-up Survey	8 Week Follow-up Survey
Assess for 7 day and 30 day point prevalence.	Assess for 7 day and 30 day point prevalence.
6 Month Follow-up Survey	6 Month Follow-up Survey
Assess for 7 day and 30 day point prevalence as well	Assess for 7 day and 30 day point prevalence as well
as prolonged abstinence.	as prolonged abstinence.

Participants are also eligible to use nicotine replacement therapy as per study guidelines. The study will provide nicotine lozenge or patch for up to 4 weeks if the participant has no medical contraindications for use.

Participants can opt in to receive text messages from the quit coaches throughout the quitting process. Quit coaches will ask participants during the coaching sessions if

they wish to receive additional, optional text messages (e.g., motivational messages, quitting tips, etc.).

5.2 Handling of Study Interventions

For a description of the intervention protocol, see section 5.1. As part of the R34 we will develop a Manual of Procedures to document all study-related policies, procedures, measures and materials. In addition, we will work with the Arizona Research Labs (ARL) to modify the ASHLine 2.0 system to collect study-related information, and contract with BMISR to create a REDCap data and participant management system that will be integrated with the ASHLine 2.0 system and the project website. ARL is responsible for programming and maintaining the ASHLine 2.0 system and the project website. Therefore, these systems will be integrated and maintained by ARL.

As this is a behavioral intervention, it is not possible to employ masking procedures with participants or study coaches. However, ASHLine staff and project staff who obtain informed consent and conduct baseline assessments and confirm consent will not know participants' study assignment prior to obtaining consent or baseline assessments.

5.3 Concomitant Interventions

Those calling the ASHLine who request only medications will be excluded (see above).

We will provide NRT to all study participants who request it, and have no medical contraindications for use. We will screen all participants for contraindications for use of NRT, and assess level of dependence to determine whether participants should use nicotine patches or lozenges. We will offer up to 4 weeks of NRT.

5.3.1 Allowed Interventions

Participants are allowed to take nicotine replacement medication as per study policies and any other medication prescribed by their physician.

5.3.2 Required Interventions

The participants must agree to be randomized to one of the two study conditions and to participate in 6 weekly sessions, and use the project website.

5.3.3 Prohibited Interventions

Participants may not be currently enrolled in the ASHLine or any other tobacco cessation treatment program or have been enrolled in the ASHLine in the past 12 months.

5.4 Adherence Assessment

Adherence will include: 1) Coach collected participant attendance of coaching sessions; 2) Participant self-reported listening to guided imagery audio files (IIC only); 3) Participant self-reported use of cognitive-behavioral techniques (CC only); and 4) Automatically collected use of the study website.

Adherence feasibility outcomes will be measured as: at least 50% of participants will complete the 6-session intervention program; 50% of IIC participants will report listening to the guided imagery audio files at least 5 times per week; and 50% will use the website at least one time.

6. STUDY PROCEDURES

The study procedures are outlined below. See also Figure 1 and Table 3.

- 1. Potential participants will call the ASHLine or study staff.
- 2. ASHLine or study staff will describe the study and screen callers for eligibility.
- Eligible participants will be consented by the ASHLine or study staff, who will also administer the baseline survey. If participants are consented by ASHLine, study staff will call participants and confirm consent.
- 4. Participants who complete the survey will be enrolled in the study and automatically randomized by the REDCap system to one of the two study conditions.
- 5. Participants will be assigned to a study coach depending on condition.
- 6. The study coach will schedule the first and subsequent telephone coaching visits.
- 7. All visits will be conducted via phone at the initiation of the study coach.
- 8. All follow-up assessments will be scheduled and conducted by project assessment staff (not study coaches).
- Study staff will administer the follow-up assessments at 8-weeks and 6-months postenrollment.
- 10. A link to a REDCap or Qualtrics online questionnaires will be sent by email at 8 weeks and 6 months post-enrollment and participants will be instructed to complete the surveys.
- 11. Participants who have not completed a survey after one week will receive a reminder email.
- 12. Participants who have not completed a survey after two weeks will receive a phone reminder and offered the opportunity to complete the survey by phone or online.
- 13. Participants who have not completed a survey after three weeks will receive a phone reminder to complete the survey.
- 14. All participants who report abstinence on the 6-month survey will be asked to perform a biochemical validation using saliva.
- 15. Participants who have not completed a survey at four weeks will be considered lost to follow-up but retained in analyses.

Table 3. Schedule of Evaluations

Assessment	Screening, Consent, Baseline, Randomization Visit 0	Treatment Visit 1 (W1)	Treatment Visit 2 (W2)	Treatment Visit 3 (W3)	Treatment Visit 4 (W4)	Treatment Visit 5 (W5)	Treatment Visit 6 (W6)	Followup (W6)	Followup (W24)
Informed Consent Form	x								
Inclusion/Exclusion Criteria	х								
Enrollment/Randomization	Х								
Demographics	Х								
Tobacco Use	х	х	х	х	х	х	х	х	х
Dependence	x							X	Х
Cravings	х							х	х
Self-Efficacy	Х							Х	х
Expectancy/Credibility	Х							Х	х
Biochemical Validation								х	х
Website Use								Х	х
Imagery File Use								Х	х
Imagery Vividness								Х	Х
Consumer Satisfaction								х	х
Treatment Administration Form		х	Х	Х	х	Х	х		
Concomitant Medications	Х	х	Х	Х	х	Х	Х	Х	х
Adverse Events		х	Х	Х	х	Х	Х		

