7.3 Adverse Events and Serious Adverse Events

An **adverse event (AE)** is generally defined as any unfavorable and unintended diagnosis, symptom, sign (including an abnormal laboratory finding), syndrome or disease which either occurs during the study, having been absent at baseline, or if present at baseline, appears to worsen. Adverse events are to be recorded regardless of their relationship to the study intervention.

A serious adverse event (SAE) is generally defined as any untoward medical occurrence that results in death, is life threatening, requires inpatient hospitalization or prolongation of existing hospitalization, results in persistent or significant disability/incapacity, or is a congenital anomaly.

It is possible that some questions about personal behaviors (e.g. smoking) might cause emotional discomfort to participants. Care will be taken to ensure that all participants understand that they may choose not to answer any question. Quitting smoking may result in physical symptoms (e.g., sleep disturbance) and changes in mood (e.g., irritability).

Participants who use NRT may experience adverse events. Most adverse events are rare. The most common adverse events are skin irritation and itching (nicotine patch), and mouth/throat soreness or ulcers (nicotine lozenges), vivid dreams and insomnia. Rarer, more serious adverse events include dizziness, headache, rapid heartbeat, and nausea. Participants will be screened for contraindications for use of NRT (e.g., recent heart attack, uncontrolled high blood pressure). Participants using NRT will be queried about AEs at each phone contact by coaches. Participants reporting AEs will be advised how to minimize side effects. Participants reporting SAEs will be advised to stop using the NRT and call 911 or their primary care physician. All participants will be given a study telephone number to contact the study staff if they have any concerns about an untoward medical event.

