7.5 Followup for Adverse Events

[name] will monitor all AEs until resolved or considered stable up to the end of the study. Information about all AEs and SAEs will be provided in annual progress reports to UA IRB and NCI.

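### No adverse-event question is scheduled after coaching Visit 6 (week 6), although sections 7.2 and 7.3 describe safety capture for the whole study

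*Combined protocol and SAP*

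**What the plan says.** Section 6, Table 3: the "Adverse Events" row is marked at Treatment Visits 1 to 6 and nowhere else. The row above it, "Concomitant Medications", is marked at Visit 0, at all six treatment visits and at both follow-ups.

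Section 3: participants receive "6 telephone coaching sessions delivered over 6 weeks by trained ASHLine or project staff", "culminating in a quit day at approximately 4 weeks post-enrollment".

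Section 5.1: "The study will provide nicotine lozenge or patch for up to 4 weeks if the participant has no medical contraindications for use". Table 2 lists NRT as a topic for the week 3 and week 4 sessions. No passage gives a start date.

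Sections 7.3 and 10.2: coaches ask about adverse events whenever they speak to the participant by phone. Participants also get a study number to call. Section 6, step 8, assigns the follow-up assessments to assessment staff and expressly not to coaches.

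Section 7.2 describes the assessment and recording of safety as continuing for as long as the study does. Section 7.3 defines an adverse event by its occurrence during the study and adds: "Adverse events are to be recorded regardless of their relationship to the study intervention". Section 7.5 says that a designated team member "will monitor all AEs until resolved or considered stable up to the end of the study".

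**The concern.** The schedule and the safety text describe different collection periods. The schedule asks about events for six weeks. The safety text covers events until the study ends, and section 7.5 promises annual reports on all of them to the IRB and the funder.

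What is at stake is how the safety record can be read. After week 6 a low count could mean few events or could mean that no one asked, and the data could not separate the two. The study supplies a product whose side effects section 7.3 itself lists, and part of its use may fall after the last enquiry. Section 9.1 presents this trial as a small-scale run of the definitive one, so a gap in the schedule is likely to be carried forward.

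**Working it through.** There is no plan figure to reproduce. The check compares passages and then does timeline arithmetic.

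**1. Is the gap real, or damage to the table?** The concomitant-medications row has marks in both follow-up columns, so those columns were read correctly. The adverse-event row is blank there.

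**2. Does other text fill it?**
- Section 6.2.4 refers back to Table 3 for the follow-up measures.
- Table 4 and the measure descriptions in section 6.2.2 contain no adverse-event item.
- The enquiry rule in 7.3 and 10.2 applies to coaches. Coaches hold six sessions over six weeks and do not run the follow-ups, so the rule does not reach them.
- What remains after week 6 is the call-in number (7.3, 10.2) and the effort to learn reasons for dropout (6.2.5). The first depends on the participant. The second covers only those who drop out.

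**3. Length of time without a scheduled question.** Last enquiry: Visit 6, week 6, assuming that sessions keep to schedule.
- On Table 3's heading for the final follow-up (W24): 24 − 6 = 18 weeks; 18/24 = 75%.
- Taking six months as 26 weeks: 26 − 6 = 20 weeks; 20/26 = 77%.

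Table 3 heads the first follow-up W6 where the text says 8 weeks. That is a separate inconsistency. The adverse-event cell in that column is blank either way.

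**4. Share of a 4-week NRT supply after the last enquiry.** The start week s is an assumption. Supply ends at s + 4, and the uncovered weeks are (s + 4) − 6, bounded by 0 and 4.

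| Assumed start | Supply ends | Weeks after last enquiry |
|---|---|---|
| Week 2 or earlier | Week 6 or earlier | 0 of 4 |
| Week 3 (first NRT discussion) | Week 7 | 1 of 4 |
| Week 4 (about the quit day) | Week 8 | 2 of 4 |
| Week 6 | Week 10 | 4 of 4 |

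**5. Participants who stop coaching.** Section 8 keeps following them with their permission, but with no coach contact they are not asked again after their last attended session. The completion target in section 5.4 is at least 50%, so it could be met with up to 50% × 120 = 60 participants missing at least one of the six enquiries. This is what the target allows, not a forecast.

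**6. Effect of asking at the two follow-ups.** Scheduled enquiry would extend from week 6 to week 24 (or 26). The 8-week contact would fall at or after the end of any supply started by week 4 (4 + 4 = 8). The recall period at the last survey would be 24 − 8 = 16 weeks, or 26 − 8 = 18, for someone who answered the 8-week survey.

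**The case against.** The best defence is that the plan is more coherent than it looks. The rule on asking is the coach rule, and Table 3 follows it exactly. Section 7.3 says what counts as an event and that it is recorded; it does not say that active questioning lasts to study end. Section 7 regards the study as very low risk. Much of the uncovered time lies after coaching and, for most assumed start weeks, after any NRT supply.

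This defence reduces the point but does not remove it. Section 7.2 sets no end to safety assessment before the study ends, and after week 6 nothing scheduled carries it out.

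Four stronger readings are tempting, and the documents do not support them:
- A reader might infer that events after the quit day depend wholly on spontaneous calls. Visits 5 and 6 follow the week-4 quit day and both include the enquiry. Withdrawal symptoms and cravings are also rated at both follow-ups (sections 6.2.2 and 9.1).
- A reader might infer that people who leave coaching early are never asked. They are asked at each session they attend.
- A reader might infer a direct breach of section 7.5. That section concerns events already known. It lends support only because no scheduled contact after week 6 asks whether they have resolved.
- A reader might infer that the later part of NRT use is certainly missed. NRT is given on request and its start is not stated, so the uncovered part may be nil.

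**Conclusion.** The point holds as a gap in scheduled enquiry and a mismatch between Table 3 and sections 7.2 and 7.3. No adverse-event question is planned for 18 of 24 weeks, or 20 of 26, and in that time new events are captured only passively or through dropout tracking. This rests on coaching ending on schedule at week 6. The NRT element is conditional: 0 to 4 of the 4 weeks, with 2 of 4 if use starts at the quit day.

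It does not show that the safety record will be misleading: there are six scheduled enquiries, a call-in number and staff trained to report. The abstinence analysis is unaffected. It is an inexpensive improvement worth making because it changes what the trial collects.

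**What to change.** Add one adverse-event item, asking about the time since last contact, to the 8-week and 6-month surveys. Mark both follow-up columns in the adverse-event row of Table 3, and extend the enquiry rule in 7.3 and 10.2 to the assessment staff. This also reaches participants who have left coaching but still answer surveys.

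The cost is one item on two surveys already sent and a little more event logging. At six months recall spans about four months, so mild or brief events will be under-reported, and reports should show those counts separately from the ones collected at coaching visits.

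Stating an active collection window ending at week 6 and rewording 7.2 and 7.3 to match would also remove the contradiction, but it would collect nothing more. No position is taken on when NRT should start or how long it should last.
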